
The period for capturing CV safety endpoints begins at randomization. The end of this time period is the date of study completion/withdrawal, with the exception that if a death has been reported in the clinical database after this time, then the death will be included in the analysis.
 
Any endpoints that occurred before the start of this time period are considered to be prior to the time period for follow-up of cardiovascular safety events, and any endpoints that occurred after the end of this time period are considered to be post the time period for follow-up of cardiovascular safety endpoints.

Time Period for Vital Status

The period for capturing vital status begins at the date of randomization. The end of this time period is defined as follows:
 
 • For all subjects known to have died, use the date of death • For all subjects who complete the study, use the study completion date (see Section 10.6.1) • For all subjects who withdraw from the study, but vital status has been ascertained, and are known to have not died – use the latest date last known to be alive. If vital status has not been ascertained following study withdrawal, use the study withdrawal date. 
Any endpoints that occurred before the start of this time period are considered to be prior to the time period for vital status, and any endpoints that occurred after the end of this time period are considered to be post the time period for vital status.

Time Period for On-treatment Cardiovascular Endpoints

The period for capturing on-treatment CV safety endpoint events begins at the treatment start date. The end of this time period is defined as follows:
 
 • For subjects whose last non-zero dose date is missing and who took randomized treatment, use date of study withdrawal/completion • For subjects continuing on study past the last non-zero dose date +28 days, use (last non-zero dose date + 28) • For subjects whose study withdrawal/completion date is on or before (last non-zero dose date +28), use date of study withdrawal/completion 
If the censoring date as defined above for on-treatment CV safety endpoints is after the censoring date as defined for the primary analysis during the time period for follow-up of CV safety endpoints,

CV Safety Endpoints

then use the censoring date for the primary analysis time period.

Any endpoints that occurred before the start of this time period are considered to be prior to the time period for on-treatment cardiovascular safety endpoints, and any endpoints that occurred after the end of this time period are considered to be post the time period for on-treatment cardiovascular safety endpoints.

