
 • Analysis of the endpoints above (except the recurrent event analysis and components of progression of CKD) will be performed individually using an analysis model identical to that described for the co-primary MACE analysis for the evaluation of superiority, using the event dates defined in Section 10.6.4. Additionally, supportive summaries and analyses for the following endpoints will be generated including fatal events which are identified only through the death endpoint page and do not have a corresponding positively adjudicated endpoint event (see Section 10.6.4): 
 ○ MI ○ Stroke ○ Thromboembolic events: Pulmonary Embolism • For purposes of time-to-event models, subjects who have never been hospitalized will be right-censored (i.e., are still considered to be at-risk) for an all-cause hospital re-admission within 30 days. • The recurrent event analysis of MACE or hospitalization for HF events will use the Prentice, Williams, Peterson (PWP) model [Prentice, 1981], based on the Cox proportional hazards model, to analyze the multiple event data. This model analyzes the time to first, second, etc. events while accounting for the correlation of events within an individual subject. Subjects are at risk for a k^{th} event only if they survived a $(k-1)^{\text{st}}$ event. For the models described below, if there are not at least 15 k^{th} events per arm, the treatment effect associated with the k^{th}, $(k+1)^{\text{th}}$, etc. events will not be estimated. All event times will be relative to randomization, as opposed to intra-event time (i.e. total times rather than gap times will be used). 
Three models will be used. The first model will estimate a common treatment effect, regardless of the number of events experienced by subjects. A second model will be run that allows the treatment effects to differ depending on the number of events experienced by subjects. A third model will be run that allows the treatment effect associated with the time to 1st MACE or hospitalization for HF to differ from a common treatment effect estimated for time to 2nd, 3rd, 4th, etc. MACE or hospitalization for HF. The common treatment effect associated with the time to 2nd, 3rd, 4th, etc. in the third model would provide support for a treatment effect on time to subsequent MACE or hospitalization for HF.
 
It is possible for a patient to die in conjunction with experiencing a series of events in a short

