
Secondary Safety Statistical Analyses: Additional CV Safety Endpoints

time frame. Ultimately, the CEC will identify the primary cause of death. For the purposes of analysis of time to first and subsequent MACE or hospitalization for HF, only those events occurring prior to and including the ‘fatal’ event will be included. For example, suppose a subject has an MI, followed by a stroke, and dies within a short time frame. If the CEC attributes the death to the MI, only the MI will be used in the analysis. If the CEC attributes the death to the stroke, both the MI and stroke would be used. If the CEC attributes the death to some cause other than the MI and stroke, all three events would be used.

- The three components of CKD progression are: confirmed 40% eGFR decline, chronic dialysis (which includes positively adjudicated cases of dialysis < 90 days and failure to initiate dialysis when indicated), and kidney transplant. Analysis of the individual components of progression of CKD will be performed individually using an analysis model identical to that described for the principal secondary CKD progression analysis for the evaluation of superiority, using the event dates defined in Section 10.6.4.
- Analyses will include only those safety endpoints occurring within the time period for follow-up of CV endpoints, with the exception of all-cause mortality, which will use the time period for vital status (see Section 10.6.4).
- For those endpoints or components of endpoints intended to go through the adjudication process, only the adjudicated results will be used.

Model Checking & Diagnostics

- Refer to [Appendix 12: Model Checking and Diagnostics for Statistical Analyses](#).

Model Results Presentation

- The summary displays of time-to-event endpoints will include a summary of the number and percentage of subjects having events. Summaries of composite endpoints will include the number and percentage of the type of first occurrence by treatment group.
- A summary of all time-to-event endpoints including the number and percentage of subjects and number of events (including first and subsequent events) by type of event will be provided by treatment group.
- Summaries of adjudication details of all-cause mortality will include the number and percentage of subjects by cause of death.

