Due to the design of the CRF, a fatal MI is reported as both an MI and a death. Both of these events will go through the adjudication process. It is possible that the MI could be negatively adjudicated, while the death is positively adjudicated with a primary cause of acute MI. The rationale for this is that the definition of a positively adjudicated MI (contained in the CEC charter) is more explicit than the definition of acute MI as a primary cause of death. Therefore, in analyses that include MI events without including all-cause mortality, the primary approach will be to include only those fatal MI events that correspond to a positively adjudicated MI event. These analyses will then be repeated for supportive purposes using all fatal MI events – including those fatal MI events only identified through a primary cause of death (i.e., acute MI) without a corresponding positively adjudicated MI event.

Additionally, a fatal MI event could have an event date that differs from the death date because the subject may have died as a result of the MI but not on the same day. For analysis of first occurrence MACE, MI or any other composite endpoint that includes both MI and death, if both the MI and death events are positively adjudicated, the MI date will be used as the event date. For analysis of CV mortality only and all-cause mortality only, the death date will be used.

Similarly, fatal stroke events are reported as both a stroke and a death. In analyses that include stroke events without including all-cause mortality, the primary approach will be to include only those fatal stroke events that correspond to a positively adjudicated stroke event. These analyses will be repeated for supportive purposes using all fatal stroke events – including those fatal stroke events only identified through a primary cause of death (i.e., stroke) without a corresponding positively adjudicated stroke event. For analysis of first occurrence MACE, stroke, or any other composite endpoint that includes stroke and death, if both the stroke and death events are positively adjudicated, the stroke date will be used as the event date. For analysis of CV mortality only and all-cause mortality, the death date will be used.

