 - If only the day of the month of death is missing, then impute the first day of the month (e.g., --FEB2016 would impute as 01FEB2016). However, if this imputed date results in a date that is prior to the latest clinic visit, telephone visit, other contact with subject visit, CV endpoint (other than death), AE or SAE date, or date last known to be alive then impute the missing day of death as equal to this date instead. For example:
 - If --FEB2016 is given as the death date and there is a non-fatal MI on 08FEB2016, then the imputed date of death would be 08FEB2016 rather than 01FEB2016 such that the death is not before the non-fatal MI.
 - If --MAR2016 is give as the death date and the latest date is a non-fatal MI on 08FEB2016 then the imputed date of death would be 01MAR2016.
 - If the month and day of the month of death are missing, then impute as 01JAN (e.g., ----2016 would impute as 01JAN2016). However, if this imputed date results in a date that is prior to the latest clinic visit, telephone visit, other contact with subject visit, CV endpoint (other than death), AE or SAE date, or date last known to be alive then impute the missing month and day of death as equal to this date instead. For example:
 - If ----2016 is given as the death date and the latest date is a non-fatal MI on 08FEB2016 then the imputed date of death would be 08FEB2016 rather than 01JAN2016 such that the death is not before the non-fatal MI.
 - If ----2017 is given as the death date and the latest date is a non-fatal MI on 08FEB2016 then the imputed date of death would be 01JAN2017.
 - For deaths that occur after subjects have prematurely withdrawn from the study, missing or partial dates will be imputed as specified above except if the imputation places the death prior to or on the premature withdrawal date. In this case the death date will be imputed as the premature withdrawal date.
- If both death and study completion/withdrawal have missing or partial dates, they will be imputed as specified (see Section 10.6.1 and Section 10.6.4). If the imputed death date is prior to the imputed study completion/withdrawal date, then the study completion/withdrawal date will use the imputed death date instead.

Missing or Partial Hospitalization End Dates

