- If hospitalization end dates are missing or partial, the following rules for missing or partial dates will be implemented as long as the imputed date is before the next hospitalization start date or study completion/withdrawal date (if there is no next hospitalization start date). If the imputed date is after the next hospitalization start date, then the date of the next hospitalization start

CV Safety Endpoints

date – 1day will be used as the hospitalization end date. If the imputed date is after the study completion/withdrawal date, then the date of the study completion/withdrawal date will be used as the hospitalization end date.
 
 ○ If only the day of the month is missing, impute the last day of the month (e.g., --MAR2016 would impute as 31MAR2016) ○ If the month and day of the month are missing, impute 31DEC (e.g., -----2016 would impute as 31DEC2016) ○ If the year, month, and day of month are missing, impute the date of study completion/withdrawal.
Order of CV Safety Endpoint Events

 • If multiple events occur on the same day or have imputed dates that place them on the same day, but it is not clear which event occurred first, then the following order will be applied: 
 1. MI 2. Stroke 3. Hospitalization for Heart Failure 4. Thromboembolic Event: DVT 5. Thromboembolic Event: VAT 6. Thromboembolic Event: PE 7. Death
CV Mortality

 • CV mortality includes all deaths indicated as having a cardiovascular primary cause of death (including fatal MI and fatal stroke events) as well as deaths with an undetermined primary cause of death that are indicated to be either presumed sudden death or presumed cardiovascular death. Deaths with an undetermined primary cause of death that are indicated to be an unknown death will not be included as a CV mortality event.
Heart Failure Events

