Non-CV mortality	Any Non-Cardiovascular primary cause of death
Unknown (sub-category of All-cause mortality)	Any Unknown primary cause of death

Events with an adjudication record, but without an investigator reported record, will also be included in the concordance summaries.

All-cause Hospitalization and All-cause Hospital Re-admission within 30 days

- All-cause hospitalization events are defined to be hospital admissions recorded on the Hospitalization eCRF form with a hospitalization duration ≥ 24 hours.
- All-cause hospital re-admissions within 30 days are defined to be hospital admissions recorded on the Hospitalization eCRF form with a hospitalization duration of ≥ 24 hours and an admission date within 30 days following a previous discharge date of an all-cause hospitalization event, where the previous hospitalization should be \geq as stated above.
- Hospitalization rate (per year) across the study = number of all-cause hospitalization events / [follow-up time (days) / 365.25].
- All-cause hospital re-admission rate (per year) across the study = number of all-cause hospital re-admissions / [follow-up time (days) / 365.25].

CV Safety Endpoints
General Definitions

 • Time to event (days) = date of event – randomization date +1 • Censored time (days) = censoring date – randomization date + 1 • First event person years = (cumulative total time to first event for subjects who have the event + cumulative total of censoring time for subjects without the event) / 365.25 • First event incidence rate (per 100 person years) = (100 * number of subjects with at least 1 event) / first event person years • First event absolute rate difference (per 100 person years) = daprodustat incidence rate (per 100 person years) – darbepoetin alfa incidence rate (per 100 person years)
Evaluation Time Periods for CV Endpoints
Time Period for Follow-up of Cardiovascular Endpoints

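### In the recurrent-event model for MACE or heart-failure hospitalization, same-day events are ranked but keep equal whole-day times, so the later one has no risk interval under the usual coding

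*SAP*

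**What the plan says.** Section 10.6.4.1 has a rule for coinciding events: "If multiple events occur on the same day or have imputed dates that place them on the same day". Where their sequence is unknown, a fixed ranking decides. It runs from MI through stroke, heart-failure hospitalization and the thromboembolic events to death. No time offset is given. Under General Definitions the same section sets the unit: "Time to event (days) = date of event – randomization date +1".

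Section 8.2.2.2 analyses MACE or heart-failure hospitalization as recurrent events with three PWP models. On the time scale it says: "All event times will be relative to randomization, as opposed to intra-event time (i.e. total times rather than gap times will be used". A subject is at risk for a k-th "event only if they survived a" (k-1)-st. If an arm has fewer than 15 k-th events, the effect for that and later events is not estimated. The third model is meant to show whether there is an effect on second and later events.

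The same section says which events of a fatal cluster count. In its example of an MI, a stroke and a death close together: "If the CEC attributes the death to some cause other than the MI and stroke, all three events would be used". By contrast, a fatal MI and its own death are merged in composites ("the MI date will be used as the event date"), and stroke and heart-failure hospitalization are treated in the same way.

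**The concern.** A ranking is enough for a time-to-first analysis, where one only needs to know which event came first. A PWP model also needs a stretch of time in which the subject is at risk for the second event. Two events on one date have equal times, so there is none. The rules followed literally would then leave out events that 8.2.2.2 wants used and that 8.2.1.2 counts when it tabulates subjects with one, two, or more than two MACE or heart-failure hospitalizations.

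At stake are the precision of the estimates for second and later events, and whether the event counts in the tables match those in the model. A stratum could pass the 15-event rule on events that are not in its likelihood. As a hypothetical case, an arm with 16 second events, 2 of them tied, passes on the table count, but only 16 - 2 = 14 enter the model.

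**Working it through.** The SAP gives no figure to reproduce here, so the check applies its rules to a case and then shows a range.

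**1. The interval.** For total-time PWP, event k has the risk interval (t(k-1), t(k)], with t = event date - randomization date + 1 (10.6.4.1). Section 10.6.4.1 gives an imputation example in which a partial death date in February 2016 follows a non-fatal MI on 8 February: "then the imputed date of death would be 08FEB2016 rather than 01FEB2016 such that the death is not before the non-fatal MI". Take an illustrative randomization date of 10 June 2015 and a death from another cause:

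- t for both events = 243 + 1 = 244.
- Event 1 (MI): (0, 244], length 244.
- Event 2 (death): (244, 244], length 0.

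The risk set at day 244 in the second-event stratum is {start < 244 ≤ stop}. The subject's own start is 244, so the subject is not in it, and (start, stop] counting-process input discards the row. Under 8.2.2.2 this death should count as a second event.

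**2. What is not affected.** An event on the day of randomization has t = 1 and interval (0, 1], which is not empty. First-event analyses use only intervals of the form (0, t] with t ≥ 1, so none is lost.

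**3. Which pairs are exposed.** Fatal events and the death attributed to them are already one event. What remains is distinct events on one date: for example a non-fatal MI and a heart-failure hospitalization with the same date from the endpoint committee, or a non-fatal event and a death from another cause. Imputation can add ties: other partial dates go to the first of the month, 1 January or the randomization date, and a partial death date can take the date of an earlier event, as above.

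**4. Size, by assumption.** If a share p of second events is lost, the standard error of the log hazard ratio in that stratum rises by about 1/√(1-p) - 1:

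- p = 0.05: 1/√0.95 - 1 = 2.6%
- p = 0.10: 1/√0.90 - 1 = 5.4%
- p = 0.20: 1/√0.80 - 1 = 11.8%

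**5. Illustrative simulation.** Assumptions, none from the SAP: 3,800 subjects, true hazard ratio 1, about 1,230 to 1,240 events, and 2%, 5% or 10% of all events followed by another on the same day. One run each, comparing tied rows dropped with tied rows shifted by 0.5 day.

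| Events followed by a tie | Second or later events | Lost | SE of log HR, second or later: dropped / shifted | Common-effect HR: dropped / shifted |
|---|---|---|---|---|
| 2% | 305 | 28 (9.2%) | 0.121 / 0.115 | 0.979 / 0.977 |
| 5% | 325 | 57 (17.5%) | 0.123 / 0.112 | 1.042 / 1.056 |
| 10% | 370 | 124 (33.5%) | 0.130 / 0.106 | 0.896 / 0.884 |

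The last row agrees with the formula: 0.130/0.106 = 1.23, and 1/√(1 - 124/370) = 1.23. The common-effect hazard ratio moves by 0.002 to 0.014.

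**The case against.** The strongest reply is that the SAP never says a row is dropped. It defines neither the intervals nor the input format, and tie handling within a subject is often left to dataset specifications. When the raw ties were passed to one Cox routine (PHReg in Python statsmodels), it kept them and returned essentially the shifted-data estimate. This stands: the exclusion comes from the (start, stop] convention, not from the SAP's text. It does not remove the point. Section 10.5.3 names SAS and also allows R, where that convention is the usual one, and whether an event counts should not turn on undocumented programming.

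A reader might infer that the lost events are the most severe presentations. The documents do not support that. Deaths attributed to an MI, stroke or heart-failure hospitalization are merged by design, so many fatal clusters lose nothing.

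A reader might also take an MI and a heart-failure hospitalization within one admission as a tie. Section 10.6.4.1 dates an investigator-reported MI by symptom onset and only heart failure by admission, and the analysis uses the committee's dates. A shared admission alone does not create a tie.

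Imputation ties are narrow as well. A death takes an earlier event's date only if that is the latest of all contacts, events and last-known-alive dates and the first-of-period date would fall before it.

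**Conclusion.** The point holds as a minor gap. SAP 10.6.4.1 and 8.2.2.2 together give the later of two distinct same-day events a zero-length risk interval. Under the usual input it is excluded, against the intention in 8.2.2.2 that it count.

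The effect falls mainly on the second- and later-event estimates of the second and third models and on agreement with the 15-event rule. The single treatment effect of the first model barely moves in the illustration. The size in this trial is unknown: every percentage above rests on an assumed tie frequency.

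Bias in the treatment effect would need same-day pairs to differ between arms, and nothing in the SAP suggests that they do. The endpoint is secondary, outside the multiplicity procedure, and compared with 0.025 for nominal significance only. No conclusion on the co-primary or principal secondary endpoints depends on it.

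**What to change.** Add to Section 8.2.2.2, with a cross-reference in 10.6.4.1:

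*For the PWP models only, distinct events of a subject on the same date are separated in the order of Section 10.6.4.1 by a cumulative offset (first event t, second t + 0.1 day, third t + 0.2 day, and so on), after merging fatal events with their attributed death; the number of events shifted is reported by arm.*

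The offset must be cumulative. If every later event moved to t + 0.1, the third of three same-day events would again have an empty interval. The next interval starts at the shifted time. Since the composite has four event types, the largest shift for one event of each is 0.3 day, so the order against events on other days is kept.

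Merging all same-day events into one would also remove the empty interval, but it would go against the intention to use each distinct event of a cluster.

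The cost is one sentence, one line of code and one count in a table, fixed before unblinding. First-event results do not change.
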